only once within each preferred term and system organ class. Key patient information for patients with an AE with an outcome of death, patients with SAEs, and patients with an AE leading to discontinuation of study medication will be listed.

Laboratory data (hematology, serum chemistry, coagulation, and urinalysis) will be converted to Système International units for reporting and processing purposes. Absolute values and changes from baseline will be presented descriptively. Laboratory data outside study specific reference ranges will be listed. Vital signs and ECG parameters will be presented descriptively.

ATI-450 Drug Concentrations and Pharmacokinetic Analyses

Plasma concentrations of ATI-450 will be summarized by nominal timepoint and day. Trough concentration versus time (Days 7, 14, 28, 42, 56, and 84) and concentration versus time (0 and 2 hours post-dose) by day (Days 1 and 84) will be displayed by linear scale.

Pharmacodynamic Analyses

The assessment of cytokines and phosphoprotein PD parameters will be described and provided in a separate report(s).

Protocol version and date: 3.0, 27July2020

SCHEDULE OF ASSESSMENTS

Table 1 Schedule of Assessments

Assessment	Screening Visit 1 Day -28 to Day -1	Visit 2 Baseline Day 1	Visit 3 Day 7	Visit 4 Day 14	Visit 5 Day 28	Visit 6 Day 42	Visit 7 Day 56	Visit 8 Day 84 (Week 12)	Visit 9 Follow-up 30 days (+ 7 days)		
			+/-1 day								
Informed Consent	X										
Eligibility Review	X	X									
RA and Other Medical History and Demographics	X										
QuantiFERON Gold Test for TB	X										
Height	X										
Weight	X								X		
Full Physical Exam ¹	X							X	X		
Limited Physical Exam		X	X	X	X	X	X				
	█	█	█	█	█	█	█	█	█		
	█	█	█	█	█	█	█	█	█		
SARS-CoV-2 Testing by RT-PCR		X									
HIV and Hep Screen	X										
Vital Signs	X	X	X	X	X	X	X	X	X		
12-Lead ECG	X	X			X			X	X		
Hematology, Coagulation, Chemistry, Lipids, and Urinalysis	X	X	X	X	X	X	X	X	X		
hsCRP	X	X	X	X	X	X	X	X	X		
	█	█	█	█	█	█	█	█			

Assessment	Screening Visit 1 Day -28 to Day -1	Visit 2 Baseline Day 1	Visit 3 Day 7	Visit 4 Day 14	Visit 5 Day 28	Visit 6 Day 42	Visit 7 Day 56	Visit 8 Day 84 (Week 12)	Visit 9 Follow-up 30 days (+ 7 days)
[REDACTED]		[REDACTED]	[REDACTED]	[REDACTED]	[REDACTED]	[REDACTED]	[REDACTED]	[REDACTED]	[REDACTED]
RAMRIS and CARLOS Hand-Wrist MRI Assessments	X ⁶							X ¹⁰	
[REDACTED]	[REDACTED]	[REDACTED]	[REDACTED]	[REDACTED]	[REDACTED]	[REDACTED]	[REDACTED]	[REDACTED]	[REDACTED]

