2 STUDY OBJECTIVES AND ENDPOINTS

The objectives and endpoints for this study are provided in [Table 2](#) below.

Table 2 Study Objectives and Endpoints

Objectives		Endpoints
Primary	
 To assess the safety and tolerability of ATI-450 plus MTX in patients with moderate to severe RA 	
 Number and percent of AEs and SAEs; mean change from baseline in laboratory values, vital signs, and ECGs
Secondary	
 To assess the PD of ATI-450 plus MTX in patients with moderate to severe RA 	
 Median percent change from baseline in high sensitivity C-reactive protein (hsCRP) levels over time Mean change from baseline in Disease Activity Score using 28 joint count-C-reactive protein (DAS28-CRP) over time Proportion of patients with DAS28-CRP below 2.6 Mean change from baseline in Rheumatoid Arthritis Magnetic Resonance Imaging Score (RAMRIS) Hand-Wrist assessments of synovitis or osteitis at Week 12 Proportion of patients with American College of Rheumatology (ACR)20/50/70 over time
	
 To assess the PK of ATI-450 in patients with moderate to severe RA who are receiving concomitant MTX 	
 ATI-450 concentrations at trough and 2 hours post-dose
Exploratory	
 To assess the PD of ATI-450 plus MTX in patients with moderate to severe RA 	
 Mean change from baseline in endogenous cytokine levels (e.g. TNF-α, IL-1β, IL-6, IL-8, IFNγ, IL-17, IL-18, IL-10, IL-1α, and IL-1RA) Mean change from pre-dose in ex vivo stimulated cytokine levels (e.g. TNF-α, IL-1β, IL-6, IL-8, IFNγ, IL-17, IL-18, IL-10, IL-1RA and IL-1α) Ex vivo stimulated phosphoprotein modulation

		
• Mean change from baseline in the cartilage loss score (CARLOS) Hand-Wrist magnetic resonance imaging (MRI) assessment of cartilage loss
--	--	-------------------------------------------------------------------------------------------------------------------------------------------------------------------------------------------

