12. Blood pressure levels (in supine position after at least 5 minutes rest): <90 mmHg or >140 mmHg for systolic blood pressure or <40 mmHg or >90 mmHg for diastolic blood pressure.
13. Has taken any of the following within the defined time period prior to screening visit:
 - Conventional synthetic disease-modifying antirheumatic drugs (DMARDs) (leflunomide, cyclosporine, azathioprine): 30 days
 - Rituximab or other B cell inhibitors: 6 months
 - Biologic DMARDs (infliximab, golimumab, adalimumab, certolizumab pegol, abatacept, and tocilizumab): 8 weeks
 - Etanercept and anakinra: 4 weeks
 - Janus kinase (JAK) inhibitors: 30 days
 - Investigational small molecules: 30 days

- Intra-articular corticosteroid injection: 30 days

14. Are currently receiving corticosteroids at doses greater than 10 mg per day of prednisone (or equivalent) or have been receiving an unstable dosing regimen of corticosteroids within 2 weeks of the screening visit.

15. Have started treatment with non-steroidal anti-inflammatory drugs (NSAIDs) or have been receiving an unstable dosing regimen of NSAIDs within 2 weeks of the screening visit.

16. Patients with history of stroke.

17. Significant cardiac disease that would affect interpretation of study data or the safety of the patient's participation in the study, per judgment of the investigator, including recent myocardial infarction or unstable angina, or heart failure with New York Heart Association Class III or IV symptoms.

18. Patients with the following screening or pre-dose ECG findings, specifically:

- Evidence of atrial fibrillation, atrial flutter, complete right or left bundle branch block, Wolff-Parkinson-White Syndrome, or other significant rhythm disturbance
- Evidence of acute ischemia
- Screening or pre-dose baseline mean QTcF >450 msec for males or >470 msec for females (use of the ECG algorithm is acceptable for this purpose)
- Personal or family history of congenital long QT syndrome or sudden death
- Any other finding that is considered clinically significant

19. Any joint procedure in past 90 days prior to screening

20. Known exposure to an individual with a confirmed, active diagnosis of COVID-19 at any time during the screening period.

21. Vaccination with a live or attenuated vaccine within 6 weeks prior to Baseline (Visit 2) or planned vaccination with these vaccines at any time during treatment or within 6 weeks following discontinuation of study medication.

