5.1 Demographics and Other Screening Assessments

Screening assessments that are also part of the safety assessments are described in [Section 5.3](#).

5.1.1 *Medical History*

Relevant medical history and current medical condition, including RA disease phenotype and duration as well as date of first diagnosis and previous treatments including any previous biologic or non-biologic therapy for RA will be recorded in the electronic case report form (eCRF).

At the baseline visit, inclusion/exclusion criteria will be reviewed and updated to ensure the patient remains qualified for the study. Significant findings that are observed after the patient has signed the ICF and prior to the first dose of study medication will be recorded as medical history on the eCRF. Any event observed after the patient has signed the ICF that meets the definition of a SAE will be recorded on the SAE eCRF.

5.1.2 *Demographics*

Demographic data, including year of birth/age, sex (at birth), and race, will be recorded in the eCRF.

5.1.3 *Tuberculosis Test*

An interferon-gamma release assay/QuantiFERON TB Gold test for active/latent TB will be performed at screening with analysis conducted by the sponsor's designated central laboratory. Patients with a negative test result will be eligible for the study.

In case of indeterminate results, the test may be repeated once. The patient can be included in the study if the repeat test is negative; however, if the repeat test is positive or indeterminate, the patient will be excluded from the study.

5.1.4 *Screening Clinical Laboratory Assessments*

Blood samples will be collected for clinical chemistry, coagulation, hematology, hsCRP, lipids, FSH, hepatitis B surface antigen, hepatitis B core antibody, hepatitis C antibody, and HIV-1/HIV-2. A serum pregnancy test will be performed on women of childbearing potential. All laboratory analyses will be performed by the sponsor's designated central laboratory.

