The investigator will record pregnancy information on the appropriate form and submit it to the sponsor within 24 hours of learning of the partner's pregnancy. The investigator will obtain informed consent from the female partner to collect information about the pregnancy and its outcome. Information on the status of the pregnant partner and the fetus will be forwarded to the sponsor. Generally, the follow-up will be no longer than 6 to 8 weeks following the estimated delivery date. Any termination of the pregnancy will be reported regardless of fetal status (presence or absence of anomalies) or indication for the procedure. Abnormal pregnancy outcomes (e.g., spontaneous abortion, fetal death, stillbirth, congenital abnormalities, ectopic pregnancy) will be considered SAEs.

5.3.4 *12-lead Electrocardiogram*

12-lead ECG will be obtained as outlined in [Table 1](#) using an ECG machine that automatically calculates the heart rate and measures PR, QRS, QT, and QTc intervals.

The ECG tracing should clearly identify the patient, include the date and time of the assessment and the signature and date of the person who made the interpretation; the tracing will be archived at the study site. Abnormal, clinically significant ECG results will be recorded as AEs.

5.3.5 *Vital Signs*

Vital signs will be measured prior to dosing and immediately following dosing in a semi-supine position after 5 minutes' rest and will include temperature, systolic and diastolic BP, pulse, and respiratory rate. Abnormal, clinically significant vital sign results will be recorded as AEs. If known, the underlying etiology for the abnormal clinically significant vital sign will be recorded as an AE rather than the vital sign itself.

5.3.6 *Physical Examination*

The complete physical examination will include assessments of the standard physical examination items, including general appearance, skin, eyes, ears, nose, throat, head and neck, heart, chest and lungs, abdomen, extremities, lymph nodes, musculoskeletal, neurological, and other body systems, if applicable, for describing the status of the patient's health.

The brief physical examination will include, at a minimum, signs of RA.

Body weight and height (height at screening only) will also be measured and recorded. The patient should be dressed in lightweight clothing, without shoes.

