8 STATISTICS

8.1 General Procedures

Analyses will be performed using SAS® (SAS Institute, Cary, NC, US) by the sponsor or its representatives.

The statistical analysis plan (SAP) will be approved prior to any lock of the study database and unblinding of the study data. The SAP will provide a detailed description of the statistical methods and expand on the details provided in the protocol.

All data will be presented by treatment group. Descriptive statistics (number of observations, mean, standard deviation, median, minimum, and maximum) will be provided for continuous variables, and counts and percentages will be presented for categorical variables.

Baseline is defined as the last non-missing measurement before or on the date of first administration of study medication.

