8.4.2 Safety Analyses

The Safety population will be used for the analysis of safety data (AEs, exposure to study medication, clinical laboratory, vital signs, and ECG).

AEs will be coded with the MedDRA. Treatment-emergent adverse events (TEAEs) are defined as AEs with an onset date on or after the date of first administration of study medication and through the completion of the last follow up visit or before the date of last administration of study medication + 30 days (whichever is later). TEAEs will be presented by system organ class and preferred term in frequency tables. Patients with multiple AEs will be counted only once within each preferred term and system organ class. Key patient information for patients with an AE with an outcome of death, patients with SAEs, and patients with an AE leading to discontinuation of study medication will be listed.

Laboratory data (hematology, serum chemistry, coagulation, lipids, and urinalysis) will be converted to Système International units for reporting and processing purposes. Absolute values and changes from baseline will be presented descriptively. Laboratory data outside study-specific reference ranges will be listed.

Vital signs and ECG parameters will be presented descriptively.

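### Two postures are prescribed for the same blood pressure reading: supine in exclusion 12, semi-supine in section 5.3.5, which also covers screening and Day 1

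*Combined protocol and SAP*

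**What the plan says.** Exclusion 12 in section 4.2 reads in part: "Blood pressure levels (in supine position after at least 5 minutes rest): <90 mmHg or >140 mmHg for systolic blood pressure". It goes on to exclude diastolic values below 40 or above 90 mmHg. The Protocol Summary repeats the criterion with the same posture and rest. Neither place names the visit at which the reading is taken.

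Section 5.3.5 describes how vital signs, including systolic and diastolic pressure, are obtained: "Vital signs will be measured prior to dosing and immediately following dosing in a semi-supine position after 5 minutes' rest". No other vital-signs method appears in the visible text.

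Two further places fix the reach of 5.3.5. Section 5.1 states: "Screening assessments that are also part of the safety assessments are described in" section 5.3. Table 1 carries one vital-signs row, marked at screening, Day 1, each treatment visit and follow-up, with no visible row for a separate supine reading.

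On the use of the data, Table 2 gives the primary safety endpoint as "Number and percent of AEs and SAEs; mean change from baseline in laboratory values, vital signs, and ECGs". Section 8.1 adds: "Baseline is defined as the last non-missing measurement before or on the date of first administration of study medication". Section 8.4.2 says: "Vital signs and ECG parameters will be presented descriptively".

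**The concern.** An entry criterion with numerical limits should be judged on a reading taken in the way the criterion specifies. Here the criterion specifies one posture and the method section another. A site that follows 5.3.5 at screening never tests exclusion 12 as worded. A site that follows exclusion 12 for its scheduled reading departs from 5.3.5.

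The stake is a clean eligibility decision for patients near a limit. Section 4 rules out waivers of enrollment criteria, and section 11.2 gives breach of key eligibility criteria as an example of an important deviation. From the scheduled reading alone, a monitor could not say whether a borderline patient was validly enrolled.

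Vital signs also feed the primary endpoint as change from baseline, so it is natural to ask whether the posture conflict carries through to that analysis. That has to be checked against the baseline rule.

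**Working it through.** The plan states no figure to reproduce: it gives no blood pressure effect size, standard deviation or test for vital signs. The check is a comparison of texts.

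**Step 1. Set the two instructions side by side.**

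| | Exclusion 12 (Protocol Summary and 4.2) | Section 5.3.5 |
|---|---|---|
| Posture | Supine | Semi-supine |
| Rest | 5 minutes as a minimum | 5 minutes |
| Visit | None named | All vital-signs visits in Table 1 |
| Timing against dose | None named | Before dosing and straight after dosing |
| Use | Entry limits | Safety endpoint |

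**Step 2. Ask whether these are two measurements or one.** Vital signs at screening are both a screening and a safety assessment, so section 5.1 sends them to section 5.3 and hence to 5.3.5. Table 1 schedules one set of vital signs at screening and one at Day 1, where eligibility is reviewed again. The visible text schedules no separate supine reading. The documents therefore attach two postures to one scheduled reading; they do not set up two readings.

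**Step 3. Effect on eligibility.** Suppose posture moves a reading by s mmHg. The patients whose classification changes at the upper systolic limit are those whose reading lies within s of 140 mmHg; the same holds at the systolic limit of 90 and the diastolic limits of 40 and 90. Their share is the probability that a screened patient's pressure falls in that band. The documents give neither s nor the distribution of pressure among screened patients, so the share cannot be derived.

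**Step 4. Effect on change from baseline.** Baseline normally comes from Day 1, with screening as fallback. Both fall under 5.3.5, as do all later visits, in both arms. If 5.3.5 is followed, every term in the change score is semi-supine. Postures mix only if a site takes the Day 1 or screening reading supine to satisfy exclusion 12 and that value becomes the baseline. Day 1 is a possible route because exclusion 12 names no visit and section 5.1.1 has the criteria reviewed again at the baseline visit.

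**Step 5. A related gap in the baseline rule.** Section 8.1 works by date: it accepts the last non-missing value up to and including the date of the first dose. Section 5.3.5 calls for a reading straight after dosing. On Day 1 that post-dose reading falls on the first-dose date and comes later than the pre-dose one. Taken literally, the rule allows it as baseline, and would select it if readings are ordered by clock time. This follows from the text whichever posture is used.

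**The case against.** The strongest reply is that 5.3.5 already governs every scheduled reading, so the endpoint is safe and only an editorial mismatch remains. On the endpoint this stands: with 5.3.5 followed, baseline and later values share one posture.

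A second reply is that a site can satisfy both texts by taking one supine reading for exclusion 12 and semi-supine readings for the scheduled vital signs. That is true, and it does no harm to the endpoint. But it relies on a reading that the visible schedule does not contain, and nothing tells the site to take it.

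A third is that vital signs are one part of a broad safety endpoint, described without a formal hypothesis, so no decision rule turns on a mean blood pressure difference. This also stands and keeps the point minor.

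A reader might infer something stronger: that sites will change posture between Day 1 and Day 7, that every later change score at those sites will be shifted, and that with about 6 placebo patients (25 × 1/4 = 6.25) an uneven spread of sites over arms could look like a treatment difference. The documents do not support this. It needs sites to depart from 5.3.5. The study-sites entry is redacted, so the number of sites is unknown. Section 6.3 is not visible, so any balancing by site cannot be checked. A percentage of patients moved across a limit could be produced only by assuming a posture shift and a pressure distribution; it would restate those assumptions and would not be evidence of harm.

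On the baseline rule, one may say that any analyst would use the pre-dose value. Perhaps so, but the stated rule does not say it. Parts of section 8.4 are redacted, and section 8.1 refers further detail to the SAP, so a narrower rule may exist there; none is visible.

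**Conclusion.** The point holds as an internal inconsistency of minor severity. Exclusion 12 and section 5.3.5 prescribe different postures, and slightly different rest wording, for the same reading. The relevant text is intact, so redaction does not explain the conflict. The consequence is for eligibility near the blood pressure limits, and its size cannot be derived from the documents. No shift in change from baseline and no difference between arms is shown; posture mixing would require a supine Day 1 or screening value to enter the analysis as baseline.

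The date-based baseline rule is a separate and more direct weakness for the same endpoint component, since it admits a post-dose Day 1 reading.

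The conclusion rests on two assumptions: that no redacted row or section schedules a supine reading, and that none defines a vital-signs baseline more narrowly.

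**What to change.** Reconcile exclusion 12, in the Protocol Summary and in section 4.2, with section 5.3.5. State one posture and one rest period, and apply them to the eligibility reading and to every scheduled reading. Which posture is for the sponsor to decide; the numerical limits are not in question here.

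Add one sentence to the baseline definition in section 8.1 and the Protocol Summary, and carry it into the SAP: for vital signs, baseline is the last reading before the first dose taken under section 5.3.5.

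The cost is small: wording in three places for posture and rest, and one sentence on baseline, at the next amendment. The sentence on baseline narrows a stated rule, so it should be recorded as a clarification of the analysis and not as an editorial correction. No procedure or visit is added.

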3 STUDY PLAN

3.1 Overall Study Design and Plan

The study visit schedule and planned assessments at each visit are detailed in [Table 1](#).

This is a Phase 2a, randomized, investigator- and patient-blind, sponsor-unblinded, parallel group, placebo-controlled study to investigate the safety, tolerability, PK, and PD of ATI-450 plus MTX versus MTX alone in patients with moderate to severe RA.

Approximately 25 patients are planned to be enrolled with the expectation that at least 15 patients will complete the 12-weeks of treatment. The study will consist of an up to 28-day screening period, a 12-week treatment period, and a 4-week follow-up period. The total duration of the study for patients remaining in the study until their final follow-up assessment will be up to 20 weeks.

The investigator will obtain signed informed consent from the patient before any study procedures are performed. For further details regarding the informed consent process, see [Section 9.3](#).

During the screening period each patient will be required to have all assessments performed as outlined in the Schedule of Assessments ([Table 1](#)). The MRI is not to be performed until the site obtains the results of the patient's hsCRP level to ensure that this assessment meets entry criteria prior to performing the MRI. The patient will have the RAMRIS Hand-Wrist assessment performed at their local institution and evaluated by a central radiology review team to determine if they meet the radiological inclusion criteria. Results for all of the screening assessments must be available at the time patient eligibility is reconfirmed prior to randomization and dosing.

Patients whose eligibility is confirmed at baseline will be randomized in a 3:1 ratio to receive either ATI-450 tablets (50 mg BID) plus MTX, or matching placebo tablets plus MTX. Study medications will be administered orally for 12 weeks. Patients will be required to remain on a stable dose of MTX (7.5 mg to 25 mg/week) and a stable dose of folic or folinic acid (≥ 5 mg/week) for the duration of the study.

Patients will attend clinic visits on Days 7, 14, 28, 42, 56, and 84 (± 1 day) for safety, efficacy, PK, and PD assessments. The morning dose of study medication will be administered in the clinic on each study visit day.

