6.4 Dose and Administration

ATI-450 will be administered as oral tablets for a total of 100 mg daily. Doses will be administered BID (50 mg \times 2). Matching placebo tablets will be administered in the same manner.

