8.4.4 Drug Concentration

Plasma concentrations of ATI-450 will be summarized by nominal timepoint and day. Trough concentration versus time (Days 7, 14, 28, 42, 56, and 84) and concentration versus time (0 and 2 hours post-dose) by day (Days 1 and 84) will be displayed by linear scale.

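### No scheduled vital-sign reading coincides with the 2-hour PK sample, and the date-based baseline could absorb the Day 1 post-dose reading

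*Combined protocol and SAP*

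**What the plan says.** **Timing of vital signs.** Section 5.3.5 takes vital signs "prior to dosing and immediately following dosing", semi-supine and after 5 minutes' rest. The Vital Signs row of Table 1 marks every visit, carries no footnote marker and gives no further time point.

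**Role in the endpoint.** The primary endpoint in Table 2 (Section 2) includes "mean change from baseline in laboratory values, vital signs, and ECGs".

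**Timing of PK.** The PK endpoint in the same table is "ATI-450 concentrations at trough and 2 hours post-dose". Section 8.4.4 adds that "concentration versus time (0 and 2 hours post-dose) by day (Days 1 and 84) will be displayed by linear scale".

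**Dosing.** Section 6.4: "ATI-450 will be administered as oral tablets for a total of 100 mg daily", split into two 50 mg doses. Section 3.1: "The morning dose of study medication will be administered in the clinic on each study visit day".

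**Baseline and analysis.** Section 8.1 takes as baseline the latest available value up to and including the calendar date of the first dose. This is a rule about dates, not clock times. Section 8.4.2 summarises vital signs descriptively. No readable text says which of the two readings at a visit enters the mean change.

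**The concern.** A pair of readings around a dose looks like a check for acute effects. For an oral tablet, a reading taken minutes after swallowing says little about what happens as the drug level rises. If ATI-450 shifted blood pressure or pulse in step with concentration, the paired readings could agree closely while a larger change at 2 hours went unmeasured. Symptomatic events would still surface as adverse events, but a silent shift might not.

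This matters because safety is the primary objective, Section 6.9 describes clinical experience with the compound as limited, and the Day 28 review of each patient's safety data uses these same readings.

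The baseline rule adds a second problem. On Day 1 the reading after the dose is the last one on the date of first administration. Applied literally, the rule can select it as the reference for all later changes.

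**Working it through.** The plan states no figure to reproduce here. Sample size was set by feasibility, and no effect size or standard deviation is given for vital signs.

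**Step 1. Schedules side by side.**

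| Measurement | Times on a dosing day | Source |
|---|---|---|
| Vital signs | Before the dose; immediately after it | Section 5.3.5, Table 1 |
| ATI-450 concentration | Trough (0 h) and 2 h | Table 2, Section 8.4.4 |

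The pre-dose times match. The post-dose times do not.

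**Step 2. Exposure at the readings: simple version.** Assume mono-exponential decline from 2 h to the next dose at 12 h, which is 10 h. Then trough / 2-hour level = 2^(−10/t½).

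| Assumed t½ (h) | 4 | 6 | 8 | 12 |
|---|---|---|---|---|
| Ratio | 0.18 | 0.31 | 0.42 | 0.56 |

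**Step 3. With absorption.** Assume one compartment, first-order absorption rate ka of 0.5, 1 or 2 per hour, t½ of 3 to 24 h, ke = ln 2 / t½ and a 12-hour dosing interval. Read the post-dose measurement as falling about 5 to 10 minutes after the dose, allowing for the rest period.

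- First dose: C(t) ∝ e^(−ke·t) − e^(−ka·t)
- Steady state: C(t) ∝ e^(−ke·t)/(1 − e^(−12ke)) − e^(−ka·t)/(1 − e^(−12ka))

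Example with t½ = 6 h and ka = 1, so ke = 0.1155:

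- First dose, 5 min against 2 h: (0.9904 − 0.9200) / (0.7937 − 0.1353) = 0.0704 / 0.6584 = 0.11.
- Steady state, trough against 2 h: (1/0.75 − 1) / (0.7937/0.75 − 0.1353) = 0.333 / 0.923 = 0.36.

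Ranges over the three values of ka, each as a fraction of the 2-hour level:

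| t½ (h) | First dose, 5 min | First dose, 10 min | Steady-state trough | Steady state, 5 min |
|---|---|---|---|---|
| 3 | 0.08–0.22 | 0.16–0.40 | 0.10–0.21 | 0.24–0.31 |
| 6 | 0.07–0.19 | 0.14–0.34 | 0.32–0.48 | 0.43–0.52 |
| 12 | 0.07–0.17 | 0.13–0.31 | 0.57–0.71 | 0.65–0.73 |
| 24 | 0.07–0.16 | 0.13–0.30 | 0.75–0.85 | 0.80–0.86 |

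The model has no lag for the tablet to disintegrate, so its early first-dose levels are, if anything, high.

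**Step 4. Reading the table.** On Day 1 the post-dose reading sees 7% to 22% of the 2-hour level at 5 minutes and at most 40% at 10 minutes. At steady state, trough is 10% to 85% of the 2-hour level, and half-life drives most of that spread. If the effect is proportional to concentration and has no delay, each 10 mmHg at 2 h would appear as about 1 to 8.5 mmHg at trough. The model's Tmax runs from 1.2 to 6.1 h over these inputs, so 2 h need not be the peak. The argument needs only that 2 h is the post-dose time at which exposure is measured.

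**Step 5. Baseline.** Day 1 has a reading before the dose and one after it, on the same date. A rule that takes the last value up to that date does not exclude the second. Moving that reading to 2 h without changing the rule would make matters worse, because a drug-exposed value could then be subtracted from every later one.

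**The case against.** **Absorption is not documented.** A reader might infer that no drug can be on board at the post-dose reading, so that it merely repeats the pre-dose one and the endpoint sees zero exposure on Day 1. The documents give no readable absorption data, and the illustration puts Day 1 exposure low but not at zero. That stronger reading fails; a small fraction of the 2-hour level is what can be defended.

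**The size rests on unseen figures.** With a long half-life, readings from Day 7 onward see most of the 2-hour exposure and little is lost at steady state. This stands. It narrows the later-visit problem but leaves Day 1.

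**Relevant text is blacked out.** Much of the background, the block after Section 5.3.6, several Table 1 rows and most of its footnotes cannot be read. A later reading, or earlier data on vital signs near peak, cannot be excluded. The explicit wording of Section 5.3.5 and the unmarked Vital Signs row make a hidden later reading less likely.

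**It is a design choice, with other safeguards.** The protocol does not contradict itself and never says the second reading is meant to catch peak effects, so one cannot say it promises reassurance that it fails to deliver. No readable passage names a haemodynamic concern. Sustained effects can show at six on-treatment visits after Day 1, and clinically significant abnormal values are recorded as adverse events. All of this stands, and it limits the severity.

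**Precision is poor.** With 25 patients randomised 3:1 there are about 19 against 6 on Day 1; with 15 completers, about 11 against 4 on Day 84. Assuming a standard deviation of 10 to 15 mmHg for change in blood pressure, the 95% half-width for the difference between arms is t × SD × √(1/n₁ + 1/n₂). On Day 1 that is 2.07 × SD × 0.468, or about 10 to 15 mmHg. On Day 84 it is 2.16 × SD × 0.584, or about 13 to 19 mmHg. A 2-hour reading would show a large effect but not resolve a modest one. That limits the benefit, but it limits every vital-sign summary in the trial equally and is no reason to measure at a less informative time.

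**Conclusion.** The point holds as a gap in scheduled measurement, and as a cheap improvement rather than a flaw that undermines the trial. On the readable text, no vital-sign reading coincides with the 2-hour PK sample on Days 1 and 84. On Day 1 the post-dose reading sees a small fraction of the 2-hour exposure under every assumption tried. At later visits the shortfall could be large or slight, and the readable text cannot settle which. What could be missed or understated is an effect tied to the post-dose rise. The documents do not support the broader inference that the endpoint is blind to drug effects on vital signs, because steady-state exposure is observed from Day 7.

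The baseline ambiguity does not depend on any pharmacokinetic assumption. It follows from the date rule together with two readings on Day 1.

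**What to change.** 1. On Days 1 and 84, take the post-dose vital signs at the existing 2-hour PK sampling time, or add one reading there.
2. Define the vital-sign baseline as the last value before the first dose, on or before Day 1. This must accompany item 1, for the reason given in Step 5.
3. Summarise pre-dose and 2-hour values separately, each as change from that baseline, and state which reading feeds the primary mean-change summary.

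**Cost.** No added visit or blood draw, and no change in sample size; doses are already taken in clinic and the 2-hour samples are already planned. Either the immediate post-dose reading is given up on those two days or one extra reading is taken on each. A minor amendment with ethics approval (Section 12) and a small data-capture change are needed. Days 7 to 56 stay as they are, so the 2-hour information would come from the first dose and the end of treatment only.
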